11.3.5.4 Post-Treatment Menses

The time to first post-treatment menses is defined as the number of days between the last dose date of study drug and the first day of a subject's first post-treatment menses in the Post-Treatment Follow-up Period based on observed AH data. Menses are defined as having at least 1 day when uterine bleeding categories of bleeding and/or spotting were reported. Truncated on-treatment menses at the last dose date, i.e., menses that are ongoing at the last dose date will be excluded, and the next occurrence of menses in the Post-Treatment Follow-up Period will be considered as the first post-treatment menses and will be used for reporting the time to first post-treatment menses. If the gap between two consecutive post-treatment menstrual cycles (or between truncated on-treatment

menstrual cycle and the next post-treatment menstrual cycle) is 1 day apart or less (i.e., out of the two consecutive cycles, the start date of the second cycle – the end date of the first cycle ≤ 2), these two menstrual cycles will be combined as one menstrual cycle in determining the first post-treatment menses.

Volume of bleeding in a subject's first post-treatment menses will be calculated and summarized.

Time to first post-treatment menses and volume of bleeding in first post-treatment menses will be summarized and analyzed separately for the following groups of subjects:

1. All subjects who entered the Post-Treatment Follow-up Period
2. Subjects who entered the Post-Treatment Follow-up Period and were amenorrhic at the Final Month in the Treatment Period. Amenorrhea is defined as in Section 11.3.2.
3. Subjects who entered the Post-Treatment Follow-up Period and achieved suppression of bleeding at the Final Month in the Treatment Period. Suppression of bleeding is defined as in Section 11.3.3.

Based on the time to first post-treatment menses during the Post-Treatment Follow-up Period, each subject will be categorized into one of the following non-overlapping categories: Study End Days 1 – 28, Study End Days 29 – 56, Study End Days 57 – 84, Study End Days 85 – 112, Study End Days 113 – 140, Study End Days 141 – 168, and Study End Days ≥ 168 . Summary tables will present the number and percentage of subjects in the specified categories.

11.3.6 Quality of Life Questionnaire

11.3.6.1 Uterine Fibroid Symptoms Quality of Life (UFS-QoL)

Improvement in quality of life will be assessed on the UFS-QoL Questionnaire (4-week recall). The change from Baseline to Month 3, Month 6, and Final Visit during the

Treatment Period will be calculated and summarized by treatment group for each of the UFS-QoL subscales (symptom severity, concern, activities, energy/mood, control, self-conscious, and sexual function) and the HRQL total. The change from Baseline in the Treatment Period will be analyzed using ANCOVA with treatment as the main effect and corresponding Baseline UFS-QoL as a covariate to compare each elagolix dose group to placebo. Missing scores will be dealt with using the methods recommended by the UFS-QoL Scoring Manual. The UFS-QoL questionnaire is presented in [Appendix A](#), and the relevant UFS-QoL Scoring Manual is presented in [Appendix B](#).

11.3.6.2 EQ-5D-5L

The EQ-5D-5L questions and relevant scoring rules are presented in [Appendix E](#).

The number and percentage of subjects with answers in each category of the EQ-5D-5L (Mobility, Self-care, Usual activities, Pain/Discomfort, and Anxiety/Depression) domains will be summarized at Baseline, each planned assessment, and Final Visit during the Treatment Period by treatment group.

Subject's responses to the EQ-5D-5L will be combined into a unique health state using a 5-digit code with 1 digit from each of the 5 dimensions at Baseline, each planned assessment, and Final Visit during the Treatment Period. The EQ-5D-5L states will be converted into a single preference-weighted health utility index score by applying country-specific weights if available or US weights if country-specific weights are unavailable.^{9,10}

The EQ VAS scale is numbered from 0 – 100, with 100 indicating the best health that a subject can imagine, and 0 indicating the worst health that a subject can imagine.

The change from Baseline to each planned assessment during the Treatment Period for health utility index score and EQ VAS will be analyzed using ANCOVA with treatment as the main effect and Baseline as a covariate to compare each elagolix dose group to placebo.

11.3.6.3 Patient Global Impression of Change (PGIC)

11.3.6.3.1 PGIC on Menstrual Bleeding Questionnaire

For PGIC on menstrual bleeding (PGIC – MB, [Appendix C](#)), the number and percentage of subjects in each response category will be summarized at Month 1, Month 3, Month 6, and Final Visit by treatment group. No statistical tests will be performed.

For PGIC – MB, the response categories of "Very Much Improved" and "Much Improved" will be combined together. The remaining five categories of the PGIC scale will be combined and labeled "Otherwise." The number and percentage of subjects with response of (a) "Very Much Improved" or "Much Improved," and (b) "Otherwise" will be summarized at Month 1, Month 3, Month 6, and Final Visit by treatment group.

Comparisons will be made using a Pearson's chi-square test or Fisher's exact test (if $\geq 20\%$ of the cells have expected counts less than 5) for Month 1, Month 3, Month 6, and Final Visit assessments in the Treatment Period.

11.3.6.3.2 PGIC on Non-Bleeding Uterine Fibroid Symptoms Questionnaire

For each of the PGIC questions on non-bleeding uterine fibroids symptoms (PGIC – NBUFS, [Appendix D](#)), the number and percentage of subjects in each response category will be summarized at Month 1, Month 3, Month 6, and Final Visit by treatment group. No statistical comparison will be performed.

For each of the PGIC – NBUFS questions, the response categories of "Very Much Improved" and "Much Improved" will be combined together. The remaining five categories of the PGIC scale will be combined and labeled "Otherwise." The number and percentage of subjects with response of (a) "Very Much Improved" or "Much Improved," and (b) "Otherwise" will be summarized at Month 1, Month 3, Month 6, and Final Visit by treatment group. Comparisons will be made using a Pearson's chi-square test or Fisher's exact test (if $\geq 20\%$ of the cells have expected counts less than 5) for Month 1, Month 3, Month 6, and Final Visit assessments in the Treatment Period.

11.3.6.4 Work Productivity and Activity Questionnaire: Uterine Fibroids (WPAI:UF)

For each of the measures as presented in the scoring guide [Appendix K](#) based on the data collected via the WPAI:UF, the change from Baseline to Month 6 and Final Visit during the Treatment Period will be summarized by treatment group. Comparisons between each elagolix dose group and placebo for each of these specific measures will be performed using one-way ANCOVA with treatment as the main effect and the corresponding score at Baseline as a covariate. The WPAI:UF is presented in [Appendix J](#), and the WPAI:UF scoring guide is presented in [Appendix K](#).

11.3.6.5 Health Care Resource Utilization Questionnaire (HCRU)

HCRU data will be summarized as observed; missing data will not be imputed. HCRU data will be summarized by treatment group at Months 1 – 6 and Final Visit. Version 1 and Version 2 of HCRU will be summarized separately. Descriptive statistics will be presented for the total number of Non-Study Health Care Practitioner Visits, overall and by the type of facility subjects were seen at. The number and percentage of subjects will also be presented by the type of Non-Study Health Care Practitioner who administered care to the subject.

The number and percentage of subjects will be presented by the type of diagnostic or therapeutic procedures performed based on HCRU at Months 1 – 6 and Final Visit during the Treatment Period. No statistical tests will be performed.

11.3.6.6 Number of Days in Hospital

Hospitalization related data will be summarized as observed; missing data will not be imputed. Hospitalization data will be summarized by treatment group in the Treatment Period based on the Adverse Events eCRF.

The number and percentage of subjects who were hospitalized or had prolonged hospitalization will be summarized by treatment group. If a subject was hospitalized or

had prolonged hospitalization multiple times during the Treatment Period, she will be counted only once.

The number of hospitalizations will be summarized by treatment group. The number of days in hospital (i.e., discharge date – admission date + 1) will be summarized by treatment group. Only hospitalizations with an admission date on or after the first dose date and within 30 days following the last dose date (i.e., first dose date \leq admission date \leq last dose date + 30) are included in the analysis of the number of days in hospital. If discharge date or admission date is missing, then the hospitalization will be excluded from the analysis of the number of days in hospital. No statistical tests will be performed.

11.4 Handling of Multiplicity

The primary comparison for all analyses will be made between elagolix 300 mg BID in combination with E2/NETA and placebo. The elagolix 300 mg BID alone group serves as a reference arm.

Therefore, no adjustment of the type I error rate (alpha) for primary analysis of the primary endpoint is needed. Ranked secondary endpoints will follow a fixed-sequence testing procedure.¹¹

12.0 Safety Analysis

12.1 General Considerations

Safety analyses will be carried out using the Safety Analysis Set, which includes all subjects who received at least one dose of study drug. Safety data will be summarized by actual treatment received. If a subject receives more than one type of study drug, safety data will be analyzed in the treatment group to which she was randomized to. All safety analyses will be based on observed data. For analyses of safety endpoints, subjects who are missing an evaluation will not be included in the analysis of that particular parameter/visit, unless otherwise specified.

For continuous variables, when the analyses of change and/or percent change from Baseline to post-baseline visit(s) are performed, the within-group change from Baseline to each relevant visit will be summarized by treatment group with the mean, SD, and 95% CIs. The between-group differences will be summarized with the mean, SE, 95% CIs, and *P* value when applicable. At each post-baseline visit, the Baseline mean and post-baseline visit mean will be calculated for all subjects with baseline and post-baseline value at that visit by treatment group.

For qualitative categorical variables, Fisher's exact test will be used to analyze between-group differences when applicable. Categorical data will be summarized by number and percentage of subjects by treatment group.

Pregnancies and outcomes will also be summarized by treatment group.

Statistical comparisons will be performed between each elagolix dose group and placebo in the Treatment Period only, unless otherwise specified. There will be no testing for safety endpoints in the Post-Treatment Follow-up Period.

Information regarding corresponding statistical methods for analyses and any additional statistical measures required for a specific variable/endpoint will be specified in the relevant sections.

12.2 Adverse Events

Adverse events (AEs) will be summarized using system organ classes (SOCs) and preferred terms (PTs) from the Medical Dictionary for Regulatory Activities (MedDRA) Version 19.0 or higher.

For each AE summary, the number and percentage of subjects experiencing at least one AE will be presented. Subjects reporting more than one AE within a SOC will be counted only once for that SOC. Subjects reporting more than one AE for a PT will be counted only once for that PT.

Treatment-emergent AEs are defined as AEs with a start date on or after the first dose of study drug. AEs starting more than 30 days following discontinuation of study drug will not be included in summaries of treatment-emergent AEs. Post-Treatment AEs are defined as AEs starting more than 30 days following discontinuation of study drug in the Treatment Period of this study.

When summarizing AEs by relationship or severity, if a subject has an event with unknown severity or relationship then the subject will be counted in the severity/relationship category of "unknown" even if the subject has a second occurrence of the same event with a severity/relationship present. The only exception is if the subject has a second occurrence of the same event with the most extreme severity (i.e., "severe") or one of the two most extreme relationship categories (i.e., "probably related" or "possibly related"). In this case, the subject will be counted under these most extreme severity/relationship categories.

Treatment Period

The number and percentage of subjects with treatment-emergent AEs will be calculated by treatment group as follows:

- Any AEs
- Any AEs by system organ class (SOC) and preferred term (PT)
- Any AEs occurring in $\geq 5\%$ of subjects by system organ class (SOC) and preferred term (PT)
- Any AEs by PT in descending frequency of elagolix 300 mg BID plus E2/NETA treatment group
- Any AEs by maximum severity
- Any AEs by maximum relationship
- Any AEs reasonably possibly related to study drug
- Any AEs leading to study drug discontinuation
- Any serious AEs (SAEs)
- Any SAEs reasonably possibly related to study drug

- Any SAEs leading to study drug discontinuation
- Any AEs of special interest as specified in [Appendix Q](#)
- Any AEs leading to death

A listing by treatment group of treatment-emergent AEs with subject IDs will be generated. Listings of all treatment-emergent SAEs, AEs leading to death, and AEs leading to study drug discontinuation will be generated.

Summary of total number of hot flush and night sweat by subject-reported severity categories, summary of total number of hot flush and night sweat by maximum subject-reported severity, and summary of time to first onset of hot flush and night sweat will be provided. Listings of subjects associated with hot flush and night sweat will also be provided.

Post-Treatment Follow-Up Period

The Post-Treatment AEs will be summarized as follows:

- Any AEs
- Any SAEs.

12.3 Laboratory Variables

Hematology, clinical chemistry, urinalysis, and endocrine panel variables collected in this study are specified in the protocol. An overall summary will be provided for all laboratory variables. For all other analysis, analysis will be performed for the following laboratory variables: lipid variables, liver variables (alkaline phosphatase, ALT, AST, bilirubin), hemoglobin, hematocrit, platelet count, and Red Blood Cell (RBC) count.

For lipid variables, in addition to low-density lipoprotein cholesterol (LDL-C), high-density lipoprotein cholesterol (HDL-C), total cholesterol, triglycerides (TG), and apolipoprotein A and B, the following ratios will be included: the ratio of total

cholesterol to HDL-C, the ratio of LDL-C to HDL-C, the ratio of TG to HDL-C, and the ratio of non-HDL-C (calculated as total cholesterol minus HDL-C) to HDL-C.

12.3.1 Analysis of Laboratory Variables

Treatment Period

All laboratory variables will be summarized with mean, median, standard deviation, minimum, and maximum by treatment group.

For continuous laboratory variables, the analyses of change (for all laboratory variables of interest) and percent change (only for lipid variables) from Baseline to each relevant visit in the Treatment Period will be performed. The mean change from Baseline to each relevant visit in the Treatment Period will be compared between each of the elagolix dose groups and placebo using one-way ANOVA with treatment group as the main effect, unless otherwise specified.

In the Treatment Period, the laboratory data will be categorized as low, normal, or high based on the normal ranges of the laboratory used in this study. The low or high laboratory values will be flagged in the data listings.

In the Treatment Period, shift tables for change from Baseline according to the normal range will be provided for laboratory parameters mentioned above. The shift tables will tabulate the number and percentage of subjects with baseline values of high or normal to post-baseline low, baseline values of low or normal to post-baseline high, baseline values of high or normal to final post-baseline low, baseline values of low or normal to final post-baseline high. The final value in the Treatment Period refers to the last non-missing value collected within 3 days following the last dose of study drug.

In the Treatment Period, shift tables for change from Baseline to the minimum, maximum, and final value will also be presented based on the Common Terminology Criteria for Adverse Events (CTCAE) v 4.0 grades⁸ for the laboratory tests. For those analytes that are not reflected in the CTCAE, Exceptions to Standard CTCAE Lab Grading Criteria for

Elagolix Studies will be used as specified in [Appendix R](#). The final value in the Treatment Period is as defined above. The number and percentage of subjects meeting the CTCAE will be summarized for hemoglobin and hemocrit by treatment group in the Treatment Period.

The number and percentage of subjects meeting the following criteria will be summarized at Baseline and each relevant visit by treatment group in the Treatment Period:

- Total cholesterol: ≤ 300 , $> 300 - \leq 400$, $> 400 - \leq 500$, and > 500 mg/dL
- HDL-C: < 40 and ≥ 40 mg/dL
- LDL-C: < 130 , $\geq 130 - < 160$, $\geq 160 - < 190$, and ≥ 190 mg/dL
- TG: ≤ 150 , $> 150 - \leq 300$, $> 300 - \leq 500$, $> 500 - \leq 1000$, and > 1000 mg/dL
- LDL-C/HDL-C ratio: ≤ 3 , and > 3
- Total cholesterol/HDL-C ratio: ≤ 4.5 , and > 4.5 .

In addition, the number and percentage of subjects who have potentially clinically significant (PCS) lipid values meeting the following criteria any time during the Treatment Period will be summarized by treatment group:

- Total cholesterol > 200 mg/dL
- LDL-C > 130 mg/dL
- LDL-C > 160 mg/dL
- HDL-C < 40 mg/dL
- TG > 150 mg/dL
- TG/HDL-C ratio > 3.5
- LDL-C/HDL-C ratio > 4 .

Plots will be provided by treatment group for HDL-C, LDL-C, triglycerides, and hemoglobin during the Treatment Period:

- Final post-baseline lab values vs. Baseline lab values;

- Final post-baseline lab values vs. Baseline lab values for subjects with NCI CTCAE Grade 3 or 4;
- Maximum post-baseline lab values vs. Baseline lab values;
- Maximum

Plots will be provided by treatment group for HDL-C, LDL-C, and triglycerides during the Treatment Period:

- Mean percent change from Baseline in lipid over month.

Post-Treatment Follow-Up Period

Laboratory data collected more than 3 days after the last dose of study drug in the Treatment Period will be included in the summary of data from the Post-Treatment Follow-up Period. Baseline for summaries/analyses in the Post-Treatment Follow-up Period is the same as Baseline for summaries/analyses in the Treatment Period.

In the Post-Treatment Follow-up Period, the following summaries will be presented by treatment group:

- During the Post-Treatment Follow-up Period, shift tables for change from Baseline to relevant Post-Treatment Follow-up visit(s) according to the normal ranges will be provided for LDL-C, HDL-C, TG, and total cholesterol.
- During the Post-Treatment Follow-up Period, shift tables for change from Baseline to relevant Post-Treatment Follow-up visit(s) will also be presented based on the CTCAE grades for LDL-C, HDL-C, TG, and total cholesterol.
- Change in liver enzymes (SGPT/ALT, SGOT/AST, total bilirubin, and alkaline phosphatase) and lipid parameters (LDL-C, HDL-C, TG, and total cholesterol) from Baseline to relevant Post-Treatment Follow-up visit(s) will be summarized by treatment group with descriptive statistics.

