8.1.8.3 Analysis of Laboratory Data and Vital Signs

[figure not shown]
Changes from the baseline to each visit in continuous laboratory and vital sign parameters will be summarized by treatment group. Treatment group differences for changes from baseline will be analyzed using a one-way ANOVA with treatment as the main effect.

Laboratory values will be categorized as low, normal or high based on normal ranges of the central laboratory used in this study. Low or high laboratory values will be flagged in the data listings.

Analysis details will be specified in the SAP.

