3.0 Introduction

This statistical analysis plan (SAP) describes the planned statistical analyses for elagolix (ABT-620) Study M12-815 titled "A Phase 3 Study to Evaluate the Efficacy and Safety of Elagolix in Combination with Estradiol/Norethindrone Acetate for the Management of Heavy Menstrual Bleeding Associated with Uterine Fibroids in Premenopausal Women." The analysis plan was created based on the Study Protocol M12-815 Amendment 3 dated 25 September 2017.

This analysis plan describes both the efficacy and safety analyses. The pharmacokinetic data will be analyzed separately and is not addressed in this SAP.

The SAS System 9.2 or above will be used to perform the statistical analyses. All statistical tests will be two-sided and a significance level of 0.05 will be used unless otherwise specified.

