4.3 Sample Size

Approximately 400 subjects will be randomized in a 1:1:2 ratio to placebo (N = 100), elagolix 300 mg BID (N = 100), or elagolix 300 mg BID plus E2/NETA (N = 200). The sample size will provide at least 90% power to detect a difference between the elagolix 300 mg BID plus E2/NETA group and the placebo group in the percentage of subjects with menstrual blood loss (MBL) volume < 80 mL during the Final Month (as defined in Section 7.2) and 50% or greater reduction in MBL volume from Baseline to the Final Month under the assumption of responder rates being 60% and 30% for elagolix 300 mg BID plus E2/NETA and placebo, respectively. The sample size determination is primarily driven by the need for a sufficient number of patients for the safety database. The above sample size was calculated using nQuery advisor 7.0.

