12.5 Vital Signs and Body Weight

Vital sign variables include pulse rate, sitting systolic blood pressure, sitting diastolic blood pressure, and oral body temperature.

Vital sign variables will be summarized with mean, median, standard deviation, minimum, and maximum by treatment group.

Analyses of mean change from Baseline to each relevant visit during the Treatment Period in vital sign variables and weight will be performed. The mean change from Baseline to each relevant visit in the Treatment Period will be compared between each elagolix dose group and placebo using one-way ANOVA with treatment as the main effect.

The number and percentage of subjects who have PCS vital sign and weight values meeting the following criteria will be summarized by treatment group. All increase/decrease is calculated from Baseline to a post-baseline visit in the Treatment Period.

The number and percentage of subjects who have a sustained PCS vital sign value and a listing of these subjects will be provided. A sustained PCS value is defined as 3 consecutive PCS values in the Treatment Period.

- Diastolic blood pressure
 - ≤ 50 mmHg and ≥ 15 mmHg decrease
 - > 90 mmHg and ≥ 15 mmHg increase
 - ≥ 100 mmHg
- Systolic blood pressure
 - ≤ 90 mmHg and ≥ 20 mmHg decrease
 - ≥ 140 mmHg and ≥ 20 mmHg increase
 - ≥ 160 mmHg
- Pulse rate
 - ≤ 45 bpm and ≥ 15 bpm decrease
 - > 100 bpm and ≥ 15 bpm increase
 - ≥ 120 bpm
- Weight
 - $\geq 5\%$ decrease
 - $\geq 7\%$ increase.

Change in vital signs from Baseline to relevant Post-Treatment Follow-up visit(s) (Post-Treatment Month 1, Month 3, Month 6, Month 9, Month 12, and Final Visit) will be summarized by treatment group with descriptive statistics.

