12.7.2 Endometrial Thickness

Analysis of change in endometrial thickness from Baseline to Month 3 and Month 6 in the Treatment Period will be performed. The mean change from Baseline to Month 3 (TAU/TVU only) and Month 6 will be compared between each elagolix dose group and placebo using one-way ANOVA with treatment as the main effect.

In addition, the number and percentage of subjects with endometrial thickness of < 8 mm, ≥ 8 mm and ≤ 12 mm, > 12 mm and ≤ 18 mm, and > 18 mm in the Treatment and Post-Treatment Follow-up Periods will be summarized by treatment group at each relevant visit in the Treatment Period. No comparison will be made for the Post-Treatment Follow-up Period.

Change in endometrial thickness from Baseline to relevant Post-Treatment Follow-up visit(s) will be summarized by treatment group with descriptive statistics.

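### Changes in laboratory values, vital signs, weight and endometrial thickness are compared with placebo without the baseline value; using it, as the SAP already does for BMD, would narrow the intervals at almost no cost

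*SAP*

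**What the plan says.** Three SAP safety sections use a treatment-only model for mean change from Baseline:

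- 12.3.1, laboratory variables including lipids and liver tests: "compared between each of the elagolix dose groups and placebo using one-way ANOVA with treatment group as the main effect".
- 12.5, vital signs and weight: "compared between each elagolix dose group and placebo using one-way ANOVA with treatment as the main effect".
- 12.7.2, endometrial thickness: each elagolix group is set against "placebo using one-way ANOVA with treatment as the main effect".

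The protocol takes the same line. Section 8.1.8.3, on laboratory data and vital signs, reads "Treatment group differences for changes from baseline will be analyzed using a one-way ANOVA with treatment as the main effect", and 8.1.8.1 makes one-way ANOVA the default for change and percent change in continuous safety variables. SAP 12.3.1 and protocol 8.1.8.1 both allow for exceptions specified elsewhere, but no section adds a baseline covariate for these variables.

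Elsewhere the SAP does adjust. ANCOVA with the baseline value is planned for BMD (12.4.1), MBL volume (11.3.1), bleeding days (11.3.3), hemoglobin (11.3.4), fibroid and uterine volume (11.3.5.1), UFS-QoL (11.3.6.1), EQ-5D-5L (11.3.6.2) and WPAI (11.3.6.4).

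**The concern.** SAP 12.1 reports between-group differences in change with a mean, standard error, 95% confidence interval and, where applicable, a P value. The choice of model therefore sets what the reader sees.

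A plain change score subtracts the whole baseline value, which fixes the slope of change on baseline at −1. When follow-up is less than perfectly correlated with baseline, that over-corrects, and part of any chance baseline difference between arms passes into the estimate. Randomization is unstratified (SAP 5.2), and two of the three arms have about 100 women each (SAP 4.3).

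The plan gives no reason for treating these variables differently from BMD, which is also a safety variable. Hemoglobin shows the inconsistency most clearly. Its monthly change is analysed by ANCOVA in 11.3.4, and it is also on the list in 12.3 that 12.3.1 sends to ANOVA. Essentially the same contrast can then appear in the report with two estimates, two intervals and two P values.

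At stake is the precision of the elagolix-versus-placebo safety contrasts. Lipids are among the safety topics of special interest (SAP Appendix Q), and SAP 4.3 says the sample size is driven mainly by the safety database.

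**Working it through.** **The plan's own figure.** The only power statement is for the primary endpoint: at least 90%, "under the assumption of responder rates being 60% and 30% for elagolix 300 mg BID plus E2/NETA and placebo, respectively", with 200 and 100 women and two-sided alpha 0.05 (SAP 3.0, 4.3).

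- Pooled rate: (100 × 0.30 + 200 × 0.60)/300 = 0.50.
- Null SE: √(0.25 × (1/100 + 1/200)) = 0.0612.
- Alternative SE: √(0.21/100 + 0.24/200) = 0.0574.
- Power: Φ((0.30 − 1.96 × 0.0612)/0.0574) = 99.9%.

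The statement holds; 90% power would need only 42 placebo subjects (47 with continuity correction). This has no bearing on the safety contrasts. For those, the documents give no SD, correlation or power.

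**Variance under the two models.** Let the SD be s at baseline and at follow-up, with correlation ρ. Per woman:

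- change-score ANOVA: 2s²(1 − ρ);
- ANCOVA: s²(1 − ρ²);
- ratio ANCOVA/ANOVA: (1 + ρ)/2.

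The arm-size factor (1/n₁ + 1/n₂) cancels, so the ratio is the same at 100:100 and 100:200. ρ is assumed:

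| ρ | 2(1−ρ) | 1−ρ² | Variance ratio | SE ratio | SE reduction | Power with ANCOVA where ANOVA has 80% |
|---|---|---|---|---|---|---|
| 0.3 | 1.40 | 0.91 | 0.65 | 0.806 | 19% | 0.935 |
| 0.5 | 1.00 | 0.75 | 0.75 | 0.866 | 13% | 0.899 |
| 0.7 | 0.60 | 0.51 | 0.85 | 0.922 | 8% | 0.860 |
| 0.8 | 0.40 | 0.36 | 0.90 | 0.949 | 5% | 0.840 |
| 0.9 | 0.20 | 0.19 | 0.95 | 0.975 | 3% | 0.820 |

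Read the other way, leaving baseline out widens intervals by 24% at ρ = 0.3 (1/0.806) and 3% at ρ = 0.9 (1/0.975). In sample-size terms, ANCOVA is worth 33%, 18% and 11% more women at ρ = 0.5, 0.7 and 0.8 (1/0.75, 1/0.85, 1/0.90).

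Simulation at 100:100:200 gave variance ratios of 0.754 at ρ = 0.5 (formula 0.75) and 0.902 at ρ = 0.8 (formula 0.90).

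**Unequal SDs.** With SD s₀ at baseline and s₁ at follow-up, and a common linear slope, the difference is

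(s₀² + s₁² − 2ρs₀s₁) − s₁²(1 − ρ²) = (s₀ − ρs₁)².

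This is never negative, so the direction does not depend on equal variances; only the size does.

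**Chance imbalance.** With equal SDs, a baseline difference D between arms shifts the change-score contrast by −(1 − ρ)D. The variance this contributes, as a share of the ANOVA variance, is (1 − ρ)²/[2(1 − ρ)] = (1 − ρ)/2. That is exactly 1 − (1 + ρ)/2. The imbalance and the lost precision are therefore one effect seen two ways and should not be counted twice.

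**The case against.** The strongest reply is that nothing here is wrong: the ANOVA is prespecified, consistent between protocol and SAP, and unbiased on average because treatment is randomized. That stands. A reader might infer a biased safety comparison; the documents support only a loss of precision.

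The size also rests on an assumed ρ, and for a stable measure with ρ of 0.8 to 0.9 the SE falls by only 3% to 5%. That stands too.

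Much of the safety reading does not depend on this model at all: shift tables, CTCAE grades, lipid thresholds, hepatotoxicity criteria, potentially clinically significant vital signs and thickness categories are untouched.

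Several further inferences are tempting but unsupported:

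- *That the answer on E2/NETA mitigation is weakened.* Mitigation is elagolix alone against elagolix plus E2/NETA. Sections 12.3.1, 12.5 and 12.7.2 compare each elagolix group with placebo only. For BMD, the outcome the objective names, 12.4.1 already has both the direct contrast and ANCOVA.
- *That all efficacy analyses adjust for baseline.* Suppression of bleeding (11.3.2.2) and the hemoglobin responder endpoint (11.3.4) use unadjusted chi-square or Fisher tests.
- *That every woman has a baseline value.* The documents do not say so. What holds is narrower: anyone with a change score has a baseline by construction, so adding the covariate drops no one.
- *That lipid percent change gains equally.* The formula covers absolute change. SAP 12.3.1 attaches the ANOVA to mean change, only protocol 8.1.8.1 extends it to percent change, and no gain was computed for it.

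Finally, ANCOVA adds a linear-baseline assumption, which matters more for skewed measures such as triglycerides or ALT, and an unadjusted difference matches the descriptive tables directly. Both are fair points, but the SAP accepts the same assumption for BMD and hemoglobin, and the descriptive tables can remain.

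**Conclusion.** The point holds as a low-cost improvement, not as an error. The planned comparisons are valid but less precise than they need to be, and the plan departs from its own practice for BMD and the continuous efficacy endpoints without giving a reason.

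The SE of an absolute-change contrast would fall by about 19% to 3% for ρ from 0.3 to 0.9. This assumes equal variances and a common linear slope, and ρ is not in the documents. The benefit is narrower intervals for the elagolix-versus-placebo safety contrasts, together with one model instead of two for hemoglobin change. These comparisons lie outside the fixed-sequence testing (SAP 11.4), so neither the primary conclusion nor the ranked secondary endpoints change.

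**What to change.** In SAP 12.3.1, 12.5 and 12.7.2, replace one-way ANOVA of change from Baseline with ANCOVA: treatment as the main effect and the parameter's own Baseline value as covariate, as in 12.4.1 and 11.3.4. For hemoglobin, let 12.3.1 refer to 11.3.4 so that change is modelled once. State in 12.3.1 which model applies to lipid percent change, since that is now left to the protocol default. Keep the unadjusted descriptive summaries.

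The cost is a SAP revision and one covariate in existing programs. Protocol 8.1.8.1 and 8.1.8.3 leave analysis details to the SAP, so a SAP change can suffice, with the departure from the protocol's named model recorded there. It should be made before the end-of-treatment analysis (SAP 4.4) gives the sponsor group-level results.
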